Anesthetic intervention 3) Anesthesia maintenance: using intravenous, volatile or Combined anesthetics for maintenance 5)
Multimodal analgesia: if no contraindications, give non-steroidal anti-inflammatory drugs 15 to 20 min before incision; Local incision infiltration or nerve block. Patient-controlled intravenous analgesia (PCA) was performed as required.
- ◆ Updated Blinding; The intervention fluid will be provided by the coordinating center and will be covered with a opaque bag.

ABSTRACT

Background

This a priori statistical analysis plan describes the relevant statistical considerations and analyzing methods for Colloid infusion for Optimal outcomes In Non-cardiac surgery (COIN) Trial.

Methods:

COIN trial aims to investigate whether the preoperative bolus administration of colloid before the induction of anesthesia reduces the postoperative complications of patients undergo non-cardiac surgery with general anaesthesia comparing to crystalloid bolus administration. The study is a parallel group, blinded, prospective, randomized controlled, multicenter trial. In total, 2020 adult (≥ 18 years old) participants scheduled for elective, non-cardiac surgery with ASA grade I-III will be enrolled. Eligible patients will be randomly assigned (at 1:1 allocation ratio) to infuse either colloid (5 ml/kg Hydroxyethyl Starch 130/0.4) or crystalloid (5 ml/kg of multiple electrolyte injection) before anaesthesia induction within 15 min.

The primary endpoint of interest is a composite measure of postoperative complications (defined as Clavien-Dindo Classification $\geq I$) within 30 days after surgery. The trial will determine whether preoperative colloids infusion can reduce postoperative complications within 30 days.

Conclusions:

This document provides a detailed statistical analysis plan for COIN.

Funding:

The trial is funded by the National Natural Science Foundation of China (81970448), the university and hospital foundation for patient outcome improvement (2021LC2202, 2022LC2213 and XJZT21L17), Shenzhen Medical Research Fund (C2401009).

Trial registration:

ClinicalTrials.gov identifier: NCT05728645. Registered on 05, 02, 2023.

Keywords:

Preoperative fluid management; Fluid bolus administration, Postoperative complications; Colloid; Crystalloid; Post-induction Hypotension; Statistical Analysis Plan

BACKGROUND

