Data will be collected prospectively at scheduled time points according to a pre-established case report form (CRF) and stored in REDCap. Baseline evaluation contains characteristic information such as demographics, comorbidities, chronic medications, preoperative lab tests and clinical evaluations, planned surgical procedures, blood pressure, oxygenation saturation before fluid bolus administration. Intraoperative anaesthesia information to be collected include monitored vital signs, anesthetic choice and dose, parameters for mechanical ventilation (tidal volume, positive expiratory pressure delivered, FiO_2), use of open labeled fluids and the use of inotropic drugs and vasopressors, intraoperative complications, procedure characteristics, etc. Postoperative management including the analgesia regimen, transition from the operating room to postoperative anaesthesia care unit (PACU), intensive care unit (ICU), or ward, and any complications of research interest will be documented.

The observation periods start from randomization to 30 days after surgery. Participants are closely monitored until hospital discharge. After discharge, follow-ups are conducted through either in-person hospital visit or telephone calls. Any postoperative complications will be recorded. The observation periods start from randomization to 30 days after surgery. Patients who experience adverse events (AEs) will be monitored until recovery or at least until having any indication of improvement in AE symptoms. All unresolved AEs must be followed up until the outcome is determined, or at least until the final follow-up visit.

All data will be meticulously recorded in CRFs. The principal investigator at each site is responsible for data accuracy. Original documents and test results will be verified before producing electronic versions. Data quality will also be monitored through random checks against original CRFs. An independent Data and Safety Monitoring Board (DSMB), composed of a statistician, CRC, and anesthesiology expert, will oversee the safety and scientific validity of the study.

STUDY OUTCOMES

Primary Endpoint

The primary endpoint is the composite of postoperative complications that occur within 30 days following surgery. Specifically, these complications are

evaluated based on the modified Clavien-Dindo Classification, with those classified as \geq I (as detailed in Table 1) being considered.

Secondary Endpoint

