In order to detect a 13% absolute reduction (from 33% to 26%) for the primary outcome of postoperative complications of Clavien-Dindo Grade \geq I up to 30 days after surgery (a risk ratio of 0.8), with 90% power and an overall type I error rate of 5%, a total of 2020 patients (1010 per arm) are required, accounting for 10% drop-out rate.

Randomisation procedure

Randomisation will occur after obtaining informed consent from the eligible patients and shortly before the index surgical procedure is due to start (last-minute randomization). Patients will be centrally allocated to treatment arms in a 1:1 ratio by permuted block randomization stratified with participant centers. To enter a patient into the COIN trial, research staff at each participant site will log on to a secure web-based randomization platform of Redcap data

entry system and obtain a unique patient identification number and allocation assignment. This information will be only revealed to the unblinded investigator who prepare the intervention fluids.

Datasets for Analyses

All statistical analyses within this study will be performed following the intention-to-treat principle. This implies that patients will be analysed in accordance with the treatment groups to which they were initially assigned, as depicted in Figure 1. It is expected that there will be either no or very minimal losses to follow-up for primary and secondary outcomes considering the prospective feature. Patients with missing primary outcome data will be excluded from the analysis (complete-case analysis approach). Missing data for baseline covariates to be included in the analysis model will be accounted for using multiple imputation.

Participation of individual patient in the study will be terminated if they (or their trusted person) withdraw consent. However, if the investigator discontinues the patient's participation, either temporarily or permanently, for reasons in the patient's best interest, especially when serious adverse events are suspected to be related to the intervention, the patient will remain in the analysis to uphold the intention-to-treat principle. Their data will continue to be collected until 30 days after surgery, which marks the final follow-up.

Modified Intent-to-Treat (m-ITT) population excludes individuals who had their

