surgical procedures canceled after randomization, patients who withdrew their consent. The as-treated population is defined by the treatment that was actually received during the trial. This takes into account any deviations from the initially assigned treatment regimen, such as crossovers to the other treatments. The Per-Protocol (PP) population consists of all patients who received the assigned treatment without significant deviations from the protocol. Specifically, the analysis will be restricted to those who completed the full-term intervention as it was initially assigned. Participants with treatment interruptions will be excluded from the PP analysis. The exclusion list will be verified by the steering committee prior to lock of the database. Analyses conducted on these dataset will be treated as supplementary analyses.

General analysis Principles

The COIN trial is designed to assess the impact of preoperative colloid infusion on the occurrence of postoperative complications in surgical patients undergoing non-cardiac surgery with general anesthesia. The estimand is the difference in the incidence of postoperative complications as defined by higher than grade I Clavien-Dindo classification at 30 days after surgery between Colloid bolus administration versus crystalloid bolus administration, in patients undergo elective non-cardiac surgery under general anesthesia. The target population is patients experienced surgery procedure. The patients have the planned surgery canceled after randomization will be excluded from the

primary analyses.

In general, categorical variables are to be compared using χ^2 test or Fisher's exact test. Continuous variables will be compared via t-test or Wilcoxon's rank-sum test. Variable normality will be assessed either via the Shapiro-Wilk test or QQ-plots and residual plots. Variable transformation such as natural logarithm or square root will be applied where necessary, or non-parametric methods (such as Wilcoxon rank sum test) shall be applied.

For the analyses of primary, secondary outcomes, and the process measures, the following information will be presented:

- 📅 The number of patients included in each analysis, by treatment arm
- 📅 A summary statistic of the outcome (such as, number (%), mean (sd), media (IQR), etc), by treatment arm
- 📅 The estimated treatment effect
- 📅 A 95% confidence interval for the estimated treatment effect
- 📅 A two-sided P value

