For all analyses, a significance level of 5% will be used. Multiple comparisons will be conducted without Type I error correction and will be interpreted as exploratory.

Data Presentation and Baseline characteristics

Baseline characteristics will be summarized using descriptive statistics for whole patients cohort and for each treatment group by mean and standard

deviation or median and interquartile range for continuous variables, and the number, frequencies, and percent for categorical variables.

Durations According to Dates

For the indexed surgery, the date of randomization or admission to the intensive care unit corresponding to the surgery date will serve as day 1.

Take, for example, the calculation of the postoperative hospital stay (in days).

The formula is: (Discharge date from hospital - Date of index surgery) + 1

Exact dates will be tracked and documented.

Analysis of the primary endpoints

The primary endpoint, incidence of postoperative complications as defined by higher than grade I Clavien-Dindo classification at 30 days after surgery will be analyzed using Chi-squared test as crude analysis. Unadjusted risk ratios with 95% confidence intervals will be estimated by two-by-two table with the use of log-Normal approximation or other approximation/numeric methods as appropriate. The effect size will be expressed as risk differences (95% confidence intervals) will be estimated using Wald's likelihood ratio approximation test or other methods appropriate, with the number needed to treat as the reciprocal of the risk difference, rounded to the nearest integer.

Secondary Analyses of the primary endpoint

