To better interpret the composite endpoints with different levels of clinical importance. We will repeat analysis of primary outcome using a hierarchical global rank scale by using win ratio method. This method put the greater weight on the more patient centered outcomes with more clinical relevant outcomes (death, life threatening complications) than transient, self-limiting complications. In the present study, the complications with higher grade of Clavien-Dindo classification will be put on higher hierarchy. The global rank endpoint will be constructed by comparing each patient in the intervention group to each patient in the control group (a total of $m \times n$ comparisons where m is the total number of patients in the intervention group and n the number of patients in the standard care group) for the prespecified order of the endpoints. Based on which patient performs better in each pair, the group they belong to would be declared the 'winner'. This would give us the total number of winners in each group and our test statistic would be based on this. In the case of the win-ratio method, for instance, the statistic would be the number of winners in the intervention group divided by the number of winners in the control group. A 95% confidence interval for the win ratio will be calculated with the bootstrap

method. To make the pairwise comparison, the priority order of endpoints are:

1. Clavien-Dindo grade V
2. Clavien-Dindo grade IVb
3. Clavien-Dindo grade IVa
4. Clavien-Dindo grade IIIb
5. Clavien-Dindo grade IIIa
6. Clavien-Dindo grade II
7. Clavien-Dindo grade I
8. No complications happened

Finally, We will repeat primary analysis on primary endpoints by using mITT, as-treated and PP data-sets.

For scenarios where events are rare in the defined order above, the following orders and composites shall be considered:

1. Clavien-Dindo grade V
2. Clavien-Dindo grade IV
3. Clavien-Dindo grade III
4. Clavien-Dindo grade II
5. Clavien-Dindo grade I
6. No complications happened

OR

1. Clavien-Dindo grade V
2. Clavien-Dindo grade III - IV

3. Clavein-Dindo grade I - II
4. No complications happened

Estimating the effect of the intervention for participants who undergo surgery under general anesthesia

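### The primary endpoint includes grade I complications where it is defined and powered but excludes them in the estimand and primary test, and the primary analysis set is not fixed either

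*SAP*

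**What the plan says.** **Threshold.** Three places count grade I as an event:

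- The Abstract (Methods) sets the composite at Clavien-Dindo grade I or above within 30 days.
- Primary Endpoint, under Study Outcomes, says complications are "evaluated based on the modified Clavien-Dindo Classification, with those classified as \geq I".
- Sample Sizes attaches the 33% and 26% rates to "postoperative complications of Clavien-Dindo Grade \geq I up to 30 days after surgery".

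Two places set the threshold above grade I:

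- The estimand, in General analysis Principles, is the difference in incidence "as defined by higher than grade I Clavien-Dindo classification at 30 days after surgery between Colloid bolus administration" and crystalloid.
- Analysis of the primary endpoints states the "incidence of postoperative complications as defined by higher than grade I Clavien-Dindo classification at 30 days after surgery will be analyzed using Chi-squared test".

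**Analysis set.** Datasets for Analyses opens with "All statistical analyses within this study will be performed following the intention-to-treat principle". General analysis Principles then says "The patients have the planned surgery canceled after randomization will be excluded from the" primary analyses. The modified ITT (mITT) set is defined by that exclusion plus withdrawn consent, and analyses on it are labelled supplementary. Secondary Analyses of the primary endpoint adds "We will repeat primary analysis on primary endpoints by using mITT, as-treated and PP data-sets". The later section on participants who undergo surgery under general anaesthesia defines mITT by removing patients without surgery and patients operated under local anaesthesia. It does not mention withdrawal.

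**The concern.** Table 1 makes grade I a category of its own, and a broad one. It takes in any departure from the normal course that is managed with antiemetics, antipyretics, analgesics, diuretics, electrolytes or physiotherapy. A patient whose worst complication is grade I is an event under Primary Endpoint and a non-event under Analysis of the primary endpoints. A programmer coding from the analysis section would test a rarer outcome than the one defined and powered.

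Corrections for Multiple Testing justifies the absence of any adjustment by there being one primary analysis of one primary outcome. With two admissible thresholds and two admissible analysis sets, that justification is weakened, and the choice could in principle be made after results are known.

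**Working it through.** **Inputs from the SAP.** Control 33%, colloid 26%, power 90%, type I error 5%, 1010 per arm and 10% drop-out (Sample Sizes); two-sided P value (General analysis Principles). Evaluable per arm: 1010 × 0.90 = 909. The difference used is 33 − 26 = 7 points.

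**Step 1: reproduce the plan's figure.** Pooled-variance formula for two proportions, with p̄ = (p₁ + p₂)/2:

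n = [1.960 √(2p̄(1−p̄)) + 1.282 √(p₁(1−p₁) + p₂(1−p₂))]² / (p₁ − p₂)²

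- p̄ = 0.295, so √(2 × 0.295 × 0.705) = 0.645.
- √(0.2211 + 0.1924) = 0.643.
- n = (1.264 + 0.824)² / 0.0049 = 890 per arm.
- With drop-out: 890/0.90 = 989 per arm, 1978 in total, about 2% below 2020. With a continuity correction, n = 919, and 919 × 1.10 = 1011 per arm, 2022 in total.

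The stated 2020 therefore follows from 33% versus 26%, rates that the SAP attaches to grade I or above.

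**Step 2: power at 909 per arm.**

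Power = Φ{[(p₁ − p₂)√n − 1.960 √(2p̄(1−p̄))] / √(p₁(1−p₁) + p₂(1−p₂))}

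For 33% versus 26%: (0.07 × 30.15 − 1.264)/0.643 = 1.316, so power is 90.6%.

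**Step 3: the literal reading, grade II or above.** The SAP gives no rate for this outcome. The only bound is that it cannot exceed the grade-I-or-above rate of 33%. The control rates below are assumptions. Two risk ratios are shown: the SAP's rounded 0.8, and 26/33 = 0.788, which its two rates imply.

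| Assumed control rate | Power, RR 0.8 | Power, RR 0.788 | Total N for 90% power, RR 0.8 |
|---|---|---|---|
| 30% | 82% | 87% | 2554 |
| 25% | 72% | 78% | 3254 |
| 20% | 60% | 66% | 4306 |
| 15% | 46% | 51% | 6056 |
| 10% | 32% | 35% | 9558 |

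Worked row, 20% versus 16%: (0.04 × 30.15 − 1.065)/0.543 = 0.260, so power is 60%. At RR 0.788 every row lies below 90.6%. In the RR 0.8 column a small part of the loss comes from rounding the risk ratio: 33% versus 26.4% already gives 86.9%.

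**Step 4: which threshold the rest of the SAP supports.** The win-ratio analysis re-analyses the primary outcome. Its first two hierarchies rank grade I apart from no complications; the third merges grades I and II, again apart from no complications. Grade I counts in all three. No section reconciles this with the higher threshold in the estimand and primary test.

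**Step 5: analysis set.** If cancelled surgeries are out of the primary analyses, the primary set already makes the main mITT exclusion, and repeating the analysis on mITT as a supplement adds little. If mITT is a genuine supplement, the primary set must include cancelled surgeries, and the exclusion sentence is wrong. Both cannot hold. The two mITT definitions share cancelled surgery but differ on withdrawn consent and local anaesthesia.

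**The case against.** The strongest reply is that the intent is evident. The Primary Endpoint section defines the outcome, the Abstract, Sample Sizes and win-ratio hierarchies agree with it, and the analysis sentence refers back to an endpoint already defined. On that reading the phrase is loose English for grade I or higher, power is 90.6%, and nothing is lost. This is probably right, and the proposed fix adopts it. It does not remove the defect: the same wording appears twice, in the estimand and in the primary test, and Scope of the Analysis plan commits the final manuscript to following the SAP strictly.

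The power figures also rest on assumed control rates and on carrying the same risk ratio to a different outcome. That is correct; they show a range and are not estimates.

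On the analysis set, the SAP explains intention-to-treat as analysis by assigned arm, which does not by itself require every randomised patient, so that sentence and the exclusion do not clash outright. The contradiction over the status of mITT remains. Cancellations are described as rare. Because the study fluid is given before induction, a cancellation after infusion could be related to treatment, but the SAP offers no figure for this.

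Finally, analysts are blinded and each Clavien-Dindo grade will be reported, so a change of threshold would be visible. That limits the risk of a selective choice but does not settle which result is primary.

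**Conclusion.** The concern holds. The SAP states two thresholds for its primary outcome, and the one in the estimand and primary test, read literally, is not the one the trial was sized for. Under grade I or above the sample size stands, with 90.6% power at 909 evaluable per arm. Under grade II or above, power would range from about 82% down to 32% for control rates of 30% down to 10% at a risk ratio of 0.8; both the rates and the constancy of the risk ratio are assumptions. The analysis-set conflict is real but should affect few patients. Because the definition of the primary outcome is at stake, the threshold must be corrected; the analysis-set wording is the lesser part.

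**What to change.** - In General analysis Principles (estimand) and in Analysis of the primary endpoints, write *grade I or higher (≥ I)*, to match the Abstract, Primary Endpoint, Sample Sizes and the win-ratio hierarchies.
- Name one primary analysis set. Either delete the sentence that excludes cancelled surgeries from the primary analyses, or declare the operated-patients set primary and stop calling it supplementary.
- Give mITT one definition that says explicitly how cancelled surgery, withdrawn consent and surgery under local anaesthesia are handled, and use it in both places.

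The cost is SAP wording only, with no change to sample size, data collection or conduct. The correction should be dated and made before unblinding.
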